10.4. Appendix 4: Contraceptive and Barrier Guidance

10.4.1. Definitions

Woman of Childbearing Potential (WOCBP)

Women in the following categories are considered WOCBP (fertile):

- Following menarche
- From the time of menarche until becoming postmenopausal unless permanently sterile (see below)
 - o A postmenopausal state is defined as no menses for 12 months without an alternative medical cause.

Protocol Number: PAL-E602-001

Version 8.0, 24 August 2023

- A high follicle-stimulating hormone (FSH) level in the postmenopausal range may be used to confirm a postmenopausal state in women not using hormonal contraception or hormonal replacement therapy (HRT). However, in the absence of 12 months of amenorrhea, confirmation with more than one FSH measurement is required. If the subject cannot meet these criteria as written, the subject will be considered to be WOCBP and pregnancy testing is required.
- Females on HRT and whose menopausal status is in doubt will be required to use one of the nonestrogen hormonal highly effective contraception methods if they wish to continue their HRT during the study. Otherwise, they must discontinue HRT to allow confirmation of postmenopausal status before study enrollment.
- o Permanent sterilization methods (for the purpose of this study) include:
 - Documented hysterectomy
 - Documented bilateral salpingectomy
 - Documented bilateral oophorectomy
 - For individuals with permanent infertility due to an alternate medical cause other than the above, (eg, Mullerian agenesis, androgen insensitivity, gonadal dysgenesis), investigator discretion should be applied to determining study entry.

Note: Documentation can come from the site personnel's review of the subject's medical records, medical examination, or medical history interview.

o If fertility is unclear (eg, amenorrhea in adolescents or athletes) and a menstrual cycle cannot be confirmed before first dose of study treatment(s), additional evaluation should be considered.

10.4.2. Contraception Guidance

CONTRACEPTIVES^a ALLOWED DURING THE STUDY INCLUDE:

Highly Effective Methods^b **That Have Low User Dependency** *Failure rate of* < 1% *per year when used consistently and correctly.*

- Implantable progestogen-only hormone contraception associated with inhibition of ovulation^c
- Intrauterine device (IUD)
- Intrauterine hormone-releasing system (IUS)^c
- Bilateral tubal occlusion
- Azoospermic partner (vasectomized or due to a to medical cause)

Azoospermia is a highly effective contraceptive method provided that the partner is the sole sexual partner of the woman of childbearing potential and the absence of sperm has been confirmed. If not, an additional highly effective method of contraception should be used. Spermatogenesis cycle is approximately 90 days.

Note: documentation of azoospermia for a male subject can come from the site personnel's review of the subject's medical records, medical examination, or medical history interview.

Highly Effective Methods^b **That Are User Dependent** *Failure rate of* < 1% *per year when used consistently and correctly.*

Combined (estrogen- and progestogen-containing) hormonal contraception associated with inhibition of ovulation^c

- -oral
- -intravaginal
- -transdermal
- -injectable

Progestogen-only hormone contraception associated with inhibition of ovulation^c

- -oral
- -injectable

Sexual abstinence

Sexual abstinence is considered a highly effective method only if defined as refraining from heterosexual intercourse during the entire period of risk associated with the study treatment(s). The reliability of sexual abstinence needs to be evaluated in relation to the duration of the study and the preferred and usual lifestyle of the subject.

- a) Contraceptive use by men or women should be consistent with local regulations regarding the use of contraceptive methods for those participating in clinical studies.
- b) Failure rate of < 1% per year when used consistently and correctly. Typical use failure rates differ from those when used consistently and correctly.
- c) Male condoms must be used in addition to hormonal contraception. If locally required, in accordance with Clinical Trial Facilitation Group (CTFG) guidelines, acceptable contraceptive methods are limited to those which inhibit ovulation as the primary mode of action.

Note: Periodic abstinence (calendar, symptothermal, post-ovulation methods), withdrawal (coitus interruptus), spermicides only, and lactational amenorrhoea method (LAM) are not acceptable methods of contraception. Male condom and female condom should not be used together (due to risk of failure with friction)

10.5. Appendix 5: Infusion Reaction Assessments and Management

NCI CTCAE version 5.0 Grading Criteria for Infusion Reactions

Infusion related reactions will be considered the adverse event and graded following the below CTCAE criteria.

Protocol Number: PAL-E602-001

Version 8.0, 24 August 2023

Grade	Description
1	Mild transient reaction: infusion interruption not indicated; intervention not indicated
2	Therapy or infusion interruption indicated but responds promptly to symptomatic treatment (e.g., antihistamines, NSAIDS, narcotics, IV fluids); prophylactic medications indicated for ≤24 hours
3	Prolonged (e.g., not rapidly responsive to symptomatic medication and/or brief interruption of infusion); recurrence of symptoms following initial improvement; hospitalization indicated for clinical sequelae
4	Life-threatening consequences: urgent intervention indicated
5	Death

Source: https://ctep.cancer.gov/protocoldevelopment/electronic applications/docs/ctcae v5 quick reference 5x7.pdf

Clinical Management Guidelines for Infusion Reactions

Unscheduled plasma PK, ADA and cytokine panel samples should be collected in the event of an infusion related reaction.

Infusion Reactions	Immediate Clinical Management	
Mild (Grade 1)	Assess and monitor subject closely.	
Mild-transient reaction; infusion interruption is not indicated; intervention is not indicated.	• Ensure equipment and medication are readily available should thereaction progress.	
*Any of the following symptoms may be observed:	• Increase monitoring of vital signs as medically indicated until the subject is deemed medically stable in the opinion of the investigator.	
Mild chills	Remain with subject until symptoms have	
Mild flushing	resolved.	
• Pruritus	If symptoms progress to Grade 2, proceed as	
• Transient rash (covering less than 10% BSA with or without symptoms)	described below.	
• Dizziness (not interfering with activity)		
Mild allergic rhinitis		
Moderate (Grade 2)	Apply Grade 1 clinical management and:	
Therapy or infusion interruption is indicated but	Stop infusion.	
subject responds promptly to treatment (such as NSAIDs, antihistamines, narcotics, IV fluids);	Consider giving diphenhydramine 50 mg IV and/or hydrocortisone sodium succinate 100 mg IV.	

Infusion Reactions

medications are indicated for less than or equal to 24 hours.

*Any of the following symptoms may be observed:

- Moderate flushing
- Pruritus
- Mild to moderate chest discomfort
- Mild to moderate back pain
- Mild to moderate nausea, vomiting, and/or diarrhea
- Transient rash (covering 10 to 30% BSA with or without symptoms)
- Dizziness (moderate unsteadiness or sensation of movement)
- Moderate dyspnea
- Urticaria (lesions covering 10 to 30% BSA)
- Moderate allergic rhinitis
- Fever 39 to 40°C
- Mild to moderate abdominal discomfort
- Mild hypotension (less than or equal to 20 mmHg drop from baseline)
- Rigors

Severe (Grade 3)

Prolonged (i.e., not rapidly responsive to symptomatic medication and/or a brief interruption of infusion); recurrence of symptoms following initial improvement; hospitalization is indicated for clinical sequelae.

*Any of the following symptoms may be observed:

- Fever greater than 40°C
- Hypoxia: decreased oxygen saturation at rest (e.g., pulse oximeter less than 88%)
- Severe rash (covering greater than 30% BSA with or without associated symptoms)
- Symptomatic bronchospasm with or without urticaria
- One or more symptoms of respiratory distress requiring treatment (e.g., repetitive cough, wheeze, throat tightness/change in voice)
- Generalized urticaria (covering greater than 30% BSA)
- Dizziness: severe unsteadiness or sensation of

Immediate Clinical Management

- If symptoms resolve within 1 hour of stopping drug infusion, may resume infusion at the following rates at the investigator's discretion:
 - o 25% of the rate at time of reaction for 5 minutes

Protocol Number: PAL-E602-001

Version 8.0, 24 August 2023

- o 50% of the rate at time of reaction for 5
- o 75% of the rate at time of reaction for 5 minutes
- o 100% of the rate at time of reaction
- Slowed infusion rates and durations beyond those above are permitted at the discretion of the investigator
- Otherwise, dosing will be held until symptoms resolve and corticosteroids, dose at the discretion of the investigator, should be added to the premedication regimen for the next scheduled dose and at subsequent E-602 doses.

Participants who develop recurrent Grade 2 toxicity despite adequate premedication should be evaluated for individual risk/benefit prior to further study treatment. A one week study drug delay may be considered.

Apply Grade 1 clinical management and:

- Stop infusion and do not restart.
- Consider giving diphenhydramine 50 mg IV and/or hydrocortisone sodium succinate 100 mg IV.
- Consider giving normal saline if needed for hypotension.
- Consider giving epinephrine 0.5 mg* intramuscularly STAT. Consider repeating epinephrine at 5-minute intervals twice more as needed (i.e., if breathing becomes more labored or level of consciousness decreases).
- Consider giving oxygen if needed for dyspnea.
- Consider giving bronchodilators if indicated.
- Initiate Emergency Response Call as appropriate if subject condition warrants.
- Hospitalization may be considered as indicated for clinical sequalae.
- If isolated Grade 3, attempt to retreat on another occasion after premedication including corticosteroids using a slower infusion rate as

Infusion Reactions	Immediate Clinical Management
movement	indicated for Grade 2.
Edema/angioedema	• If Grade 4 or recurrent Grade 3, permanently
• Uncontrolled hypotension (more than 20 mmHg drop from baseline) requiring therapy	discontinue study treatment.
Severe nausea, vomiting, and/or diarrhea	
	*Note: epinephrine 1:1,000 = 1 mg/mL and
Severe (Grade 4)	epinephrine $1:10,000 = 1 \text{ mg/}10 \text{ mL}$
Life-threatening consequences: urgent intervention indicated	
*Any of the following symptoms may be observed:	
Cyanosis	
• Life-threatening hypoxia or airway compromise	
Severe angioedema (periorbital/facial)	
Altered level of consciousness	

Protocol Number: PAL-E602-001

Version 8.0, 24 August 2023

^{*}Symptoms noted are intended as potential examples at each grade. Severity grading of the infusion related reaction will be based on the investigator's judgement per CTCAE v5.0.

TEAE	Treatment-Emergent Adverse Event
TLFs	Tables, Listings, and Figures
ULN	Upper Limit of Normal
WHO	World Health Organization

1 INTRODUCTION

This Statistical Analysis Plan (SAP) describes the statistical methodology and analyses to be conducted for the protocol PAL-E602-001. This document may include modifications to the analyses outlined in the protocol. Any major modifications will be documented in the SAP and described in the Clinical Study Report (CSR).

The current SAP is based on protocol v8.0 dated August 24, 2023. A summary of all approved SAP versions is provided below.

Table 1. Summary of the Approved SAP versions

Version	Approval Date	Key Changes	Rationale
1.0	30-Jul-2024	NA	Original SAP

2 STUDY OVERVIEW

2.1 Study Design

This is a Phase 1/2, first-in-human (FIH), open-label, dose escalation and dose expansion study of E-602, administered as a single agent and in combination with cemiplimab, to evaluate the safety, tolerability, pharmacokinetics (PK), pharmacodynamics, and antitumor activity in subjects with advanced cancers.

Each treatment cycle consists of 21 days. E-602 will be administered on Days 1, 8, and 15 of each cycle. Cemiplimab, if given, will be administered on Day 1 of each cycle.

Phase 1 Dose Escalation

The Phase 1 portion of the study follows a modified 3+3 design. Five planned escalating dose cohorts of E-602 monotherapy and 2 planned escalating dose cohorts of combination therapy will be enrolled. The dose for E-602 in the combination cohorts will be initiated at dose level(s) that have previously completed dosing and dose limiting toxicity (DLT) assessments (Cycle 1) as monotherapy. The maximum duration of treatment for each subject will be 1 year. No intrasubject dose escalation of E-602 will be permitted.

Table 1. Planned Escalating Dose Cohorts for Phase 1

Cohort	Number of Subjects	Dose of E-602	Frequency of E-602	Dose of Cemiplimab	Frequency of Cemiplimab
101	3 – 6	1 mg/kg	once a week	n/a	n/a
102	3 – 6	3 mg/kg	once a week	n/a	n/a
103	3 – 6	10 mg/kg	once a week	n/a	n/a
104	3 – 6	20 mg/kg	once a week	n/a	n/a
105	3 – 6	30 mg/kg	Once a week	n/a	n/a
111	3 – 6	20 mg/kg	once a week	350 mg	once every 3 weeks
112	3 – 6	to be determined	once a week	350 mg	once every 3 weeks

Phase 2: Dose Expansion

Phase 2 consists of dose-expansion disease cohorts in subjects with 3 types of advanced tumors: melanoma, non-small cell lung cancer (NSCLC), and the third type to be determined (ovarian, colorectal, pancreatic, breast, gastric/esophagogastric junction [EGJ], head and neck, or urothelial) based on available data including the Phase 1 results. Simon's minimax 2-stage design will be used for each cohort. Each disease cohort (monotherapy or combination) may be evaluated separately.

[figure not shown]
Study Monitoring and Tumor Assessments

A Safety Data Review Committee (SDRC) consisting of the principal investigators and members of the Sponsor will be formed and will meet regularly to review ongoing safety data. The committee will oversee subject safety and make recommendations to the Sponsor for all cohort dosing and dose escalation decisions.

Subjects will undergo radiological tumor assessment at baseline during screening (up to 35 days prior to Cycle 1, Day 1), 9 weeks (± 1 week) after the first dose and every 9 weeks (± 1 week) thereafter regardless of treatment delays until the End of Treatment (EOT) visit. An examination at EOT visit should be performed unless the subject already has radiographic confirmation of progressive disease (PD) within 4 weeks of the EOT visit. Response to treatment will be evaluated using the Response Evaluation Criteria in Solid Tumors (RECIST) Version 1.1 and Immunotherapy Response Evaluation Criteria in Solid Tumors (iRECIST).

The study schema is provided in Figure 1.

Figure 1 Study Schema

2.2 Study Objectives and Endpoints

The objectives of the study are to evaluate the safety, tolerability, preliminary efficacy, PK, and pharmacodynamics of E-602, as a single agent or in combination with cemiplimab, for the treatment of subjects with advanced tumors.

Table 2. Summary of Study Objectives and Endpoints

Objectives	Endpoints	
Dose Escalation Phase (Phase 1)		
Primary		
 To evaluate the safety and tolerability of E-602 as monotherapy in subjects with advanced cancers. To evaluate the safety and tolerability of E-602 in combination with cemiplimab in subjects with advanced cancers. 	 Incidence of adverse events (AEs) and serious adverse events (SAEs) graded according to National Cancer Institute (NCI) Common Terminology Criteria for Adverse Events (CTCAE) v5.0. Incidence and nature of dose limiting toxicities (DLTs) within a modified 3+3 trial design. 	
To determine the maximum tolerated dose (MTD) and/or recommended Phase 2 dose (RP2D) of E-602 as monotherapy.	The MTD and/or RP2D based on occurrence of DLTs within a modified 3+3 design.	
• To determine the MTD and/or RP2D of E-602 in combination with cemiplimab.		
Secondary		
 To assess the PK of E-602 as monotherapy. To assess the PK of E-602 in combination with cemiplimab. To evaluate the immunogenicity of E-602 	• Noncompartmental PK parameters of E-602 as monotherapy and in combination with cemiplimab, including the maximum plasma concentration (C _{max}) and area under the plasma concentration-time curve (AUC).	
To evaluate preliminary antitumor activity of E-602 as monotherapy in subjects with advanced cancers.	 Number and percentage of subjects who develop detectable antidrug antibodies (ADA). 	
To evaluate preliminary antitumor activity of E-602 in combination with cemiplimab in subjects with advanced cancers.	Objective response rate (ORR) of confirmed complete response (CR) and partial response (PR) using RECIST v1.1 and iRECIST.	
	• Duration of response (DoR).	
	 Progression-free survival (PFS), defined as the time from the first dose to first evidence of radiographically detectable disease or death from any cause, whichever occurred first. Overall survival (OS). 	

Objectives	Endpoints
Dose Expansion Phase (Phase 2)	
Primary	
 To evaluate the preliminary antitumor activity of E-602 as monotherapy in subjects with advanced cancers. To evaluate the preliminary antitumor activity of E-602 at the combination RP2D in combination with cemiplimab in subjects with advanced cancers. 	 ORR of confirmed CR or PR. DoR of confirmed CR or PR. PFS. OS.
Secondary	
 To evaluate the safety and tolerability of E-602 as monotherapy in subjects with advanced cancers. To evaluate the safety and tolerability of E-602 in combination with cemiplimab in subjects with advanced cancers. To assess the PK of E-602 as monotherapy. To assess the PK of E-602 in combination with cemiplimab. To evaluate the immunogenicity of E-602 	 Incidence of AEs and SAEs graded according to NCI CTCAE v5.0. Noncompartmental PK parameters of E-602 as monotherapy and in combination with cemiplimab. including C_{max} and AUC. Number and percentage of subjects who develop detectable ADA.

Objectives	Endpoints	
Phase 1 and Phase 2		
Exploratory		
• To evaluate exploratory pharmacodynamic biomarkers of E-602 activity as monotherapy.	 Immune cell desialylation and activation using fluorescence-activated cell sorting (FACS) 	
To evaluate exploratory pharmacodynamic biomarkers of E-602 activity in combination with	• Immune cell gene expression profiling (RNAseq; Phase 1 E-602 monotherapy only)	
cemiplimab.	Changes in cytokine levels	
	Changes in circulating tumor DNA	
	Changes in tumor desialylation by immunohistochemistry (IHC)	
	Tumor IHC analysis for immune modulation of different immune cell subtypes	
	• Tumor gene expression and mutation profiling	
	Glycoproteomic profiling	
	• Genetic variation or single nucleotide polymorphisms (SNPs) in select genes (e.g. glycogenes) (Phase 1 combination and Phase 2 only)	

2.3 Sample Size Determination

Dose escalation for all cohorts will utilize a modified 3 + 3 design. Five dose escalation cohorts are planned for E-602 monotherapy for a total of up to 30 subjects. Two dose cohorts are planned for the E-602 and cemiplimab combination therapy for a total of up to 12 subjects. Any Phase 1 cohort may be backfilled up to 15 subjects in a dose cohort (dose escalation and backfill) to obtain additional safety, PK and pharmacodynamic data at a particular dose level.

For each cohort in Phase 2, Simon's minimax 2-stage design will be used. Sixteen subjects will be enrolled in the first stage. If ≥ 2 of 16 subjects respond, Stage 2 will be opened to enroll an additional 15 subjects for a total of 31 subjects in the cohort. At the end of Stage 2, if ≥ 6 of 31 subjects respond, the treatment will be considered promising for further evaluation. Within each cohort, the design has 80% power and a type I error rate of 0.1 to test the null hypothesis that the response rate is $\leq 10\%$ against the alternative hypothesis of $\geq 25\%$.

3 ANALYSIS POPULATIONS

This section defines the analysis populations to be used for the planned statistical analyses. Study treatment is defined as E-602 monotherapy or E-602 in combination with cemiplimab. Date of first dose of study treatment is defined as the first dose of E-602 for monotherapy and first dose of cemiplimab for combination.

3.1 Safety Population (Intent to Treat)

All subjects who have received any dose of E-602. The Safety Analysis Population will be used for safety analyses. Safety Analysis Population may be further defined by the phase of the study, dose, tumor type, and therapy received (monotherapy or combination therapy).

3.2 DLT Evaluable Population (Phase 1 Dose Escalation)

All subjects treated in the dose escalation part who have had a DLT within Cycle 1 on study or without a DLT but completed safety assessments through Cycle 1 (3 doses of E-602 administered for monotherapy cohorts and 3 doses of E-602 and 1 dose of cemiplimab administered for combination therapy cohorts). The DLT Evaluable Set will be defined for each dose cohort. Subjects who discontinue prior to completing Cycle 1 (3 doses of E-602 administered for monotherapy cohorts and 3 doses of E-602 and 1 dose of cemiplimab administered for combination therapy cohorts) for reasons other than toxicity may be replaced.

3.3 Efficacy Evaluable Population

All subjects who receive any dose of study treatment, have measurable tumor lesions at baseline, and have at least one post-baseline disease assessment per RECIST v1.1.

3.4 Pharmacokinetic (PK) Evaluable Population

All subjects in the Safety Analysis Population for whom adequate E-602 plasma concentration data are available.

3.5 Pharmacodynamic Evaluable Population

All subjects in the Safety Analysis Population for whom there is at least one non-missing baseline measurement and at least one non-missing post-baseline measurement for the pharmacodynamic parameter.

4 CLINICAL OUTCOME VARIABLES

This section provides endpoint definitions. For endpoints based on tumor assessments, such as ORR, BOR, DoR, and PFS, investigator assessments are used per RECIST v1.1.

4.1 Primary Efficacy Endpoint

Objective Response Rate (ORR)

The ORR is defined as the proportion of subjects whose overall response is a confirmed CR or PR per RECIST v1.1. To be assigned a status of confirmed PR or CR, changes in tumor measurements must be confirmed by repeated assessments at least 4 weeks (28 days) after the criteria for response are first met. Tumor assessments after the initiation of new anticancer therapy should not be used to derive the ORR.

In addition to ORR, Best Overall Response (BOR) will be summarized based on the response assessments from all visits for each subject. BOR is defined as the best response per RECIST v1.1 in the order of CR, PR, stable disease (SD), PD, not evaluable (NE). For the BOR to be CR or PR, responses need to be confirmed. For the BOR to be SD, measurements must have met the SD criteria at least once at a minimum of 6 weeks from the start of treatment. Tumor assessments after PD per RECIST v1.1 or the initiation of new anti-cancer therapy (NACT) should not be used to derive the BOR.

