4.1.2. Continued Treatment Beyond Disease Progression

Each subject will receive the study treatment for 1 year, unless the treatment is discontinued for any of the reasons listed in Section 7.1.

Treatment beyond progressive disease (PD) will be allowed as per iRECIST guidelines (Seymour 2017). The following criteria must be met for continued use of the study treatment beyond PD:

- Absence of symptoms and signs indicating clinically significant progression of disease
- No decline in the Eastern Cooperative Oncology Group (ECOG) performance status
- Absence of symptomatic rapid disease progression requiring urgent medical intervention (e.g., symptomatic pleural effusion, spinal cord compression).

At the time of radiographic progression of disease, a subject will be reconsented with emphasis on the FDA-approved therapy and potential clinical benefit that the subject may be foregoing to continue treatment.

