7.1. Discontinuation of Study Treatment

Subjects will permanently discontinue study treatment for any of the following:

• PD (confirmed PD for subjects who continued treatment beyond PD, see Section 4.1.2)

Protocol Number: PAL-E602-001

Version 8.0, 24 August 2023

- Initiation of alternative cancer therapy
- Unacceptable toxicity including permanent discontinuation criteria defined in Section 6.5
- Subject's decision to discontinue treatment
- Withdrawal of consent
- Investigator's decision to discontinue treatment
- Sponsor's decision to discontinue treatment
- Inability of the subject to comply with the requirements of the study
- Completion of maximum treatment duration of 1 year from Cycle 1 Day 1

If study treatment is permanently discontinued, the subject will return for an EOT visit as well as 30 days and 90 days after the last dose for safety follow-up, as indicated in the SoA (Section 1.3). In addition, the subject will be contacted every 3 months for disease status (if the discontinuation is not due to progression of disease) and survival, until 15 months after Cycle 1 Day 1.

Subjects treated in the Phase 1 dose escalation part of the study will discontinue treatment if he/she experience DLT(s) during Cycle 1 (see Section 4.1.5).

For all subjects, see Section 6.5 for toxicity-related treatment-discontinuation criteria.

For subjects receiving the combination therapy of E-602 and cemiplimab, both treatments should be discontinued simultaneously.

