8.1. Efficacy Assessments

Planned timepoints for all efficacy assessments are provided in the SoA.

Subjects will undergo radiological tumor assessment at baseline during screening (up to 35 days prior to Cycle 1, Day 1), 9 weeks (± 1 week) after the first dose and every 9 weeks (± 1 week) thereafter regardless of treatment delays until the EOT visit. An examination at EOT visit should be performed unless the subject already has radiographic confirmation of PD within 4 weeks of the EOT visit.

Tumor assessment should include contrast-enhanced computed tomography (CT, preferred) or magnetic resonance imaging (MRI) of the chest, abdomen, and pelvis. The same method (positron emission tomography [PET]/CT, MRI, or CT) and the same technique should be used to characterize each identified and reported lesion throughout the study. Lesions in a previously irradiated field may be assessed as target lesions if progression since irradiation has been demonstrated.

Response to treatment will be evaluated using the RECIST version 1.1 (Eisenhauer 2009) and iRECIST (Seymour 2017). Subject responses will be classified as progressive disease (PD), stable disease, partial response (PR), and complete response (CR). A per timepoint response of Stable Disease requires a minimum of 56 days between two measures. To assess a Best Overall Response (BOR) of CR or PR per RECIST version 1.1, confirmation of the CR or PR is required at the subsequent timepoint at least 4 weeks later.

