4.2 Secondary Efficacy Endpoints

Duration of Response (DoR)

Duration of response is defined as the time from the start date of first observed CR or PR (subsequently confirmed) to the date of first documented radiographical progression of disease using RECIST v1.1 or death from any cause, whichever comes first. DoR will be calculated for subjects who are responders, i.e., those who achieve a confirmed CR or PR.

DoR in days will be calculated as:

DoR (days) = [Date of PD, or Death, (whichever is earlier)] – (First Date of PR/CR) + 1 DoR in months will be calculated as:

DoR (months) =
$$[12 \times DoR (days)]/365.25$$

Responders who have not experienced disease progression or death at the time of the analysis will be censored at the date of the last tumor assessment. If no tumor assessments are available after the date of the first occurrence of response, the subject will be censored on the date of the first occurrence of the response.

Progression-Free Survival (PFS)

Progression-free survival is defined as the time from the date of first dose (study day 1) of study treatment to the first documented radiographical progression of disease using RECIST v1.1, or death from any cause, whichever comes first.

PFS in days will be calculated as:

PFS (days) = [Date of PD or Death (whichever is earlier)] – (First Dose Date) + 1

PFS in months will be calculated as:

PFS (months) =
$$[12 \times PFS (days)]/365.25$$

The following table summarizes the PFS censoring rules:

Table 3: Progression-Free Survival Censoring Rules

	Primary Analysis (Censoring Rules)	Sensitivity Analysis (Censoring Rules)
No PD, No death	Censored at last tumor assessment. If no evaluable tumor assessment, censored on the first dose date.	Censored at last tumor assessment. If no evaluable tumor assessment, censored on the first dose date.
PD or death after 1 missed tumor assessment	PFS event at the date of PD or death	PFS event at the date of PD or death
PD or death after 2 or more missed tumor assessments	Censored at last tumor assessment prior to PD or death	PFS event at the date of PD or death
PD or death after NACT	Censored at the last tumor assessment prior to NACT	PFS event at the date of PD or death
No PD, no death, NACT initiated	Censored at the last tumor assessment prior to NACT	Censored at last tumor assessment regardless of NACT

Overall Survival (OS)

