6.3 Efficacy Analyses

The primary efficacy analyses will be based on the efficacy evaluable population. For each tumor indication, subjects administered the same study treatment may be combined for analysis purposes, regardless of study phase. All data from scheduled or unscheduled tumor assessments will be included in the efficacy analyses except for tumor assessments after the initiation of new anti-cancer therapy for the ORR and DoR endpoints as described in Section 4.

Sensitivity efficacy analysis may be performed based on the ITT Population if it is sufficiently different from the efficacy evaluable population and the additional analysis may be informative. Subjects with no measurable baseline disease or no evaluable post-baseline disease assessments (i.e., NE) will be considered non-responders and included in the denominator in the calculation of the ORR for the ITT population.

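### The SAP stops best overall response at RECIST progression but not the ORR, so a response after progression can enter the primary ORR with a negative duration of response

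*SAP*

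**What the plan says.** SAP 4.1 defines ORR as the proportion of subjects with a confirmed CR or PR under RECIST v1.1. It gives one limit on which scans count: "Tumor assessments after the initiation of new anticancer therapy should not be used to derive the ORR". The next paragraph introduces BOR as a further summary and sets a wider limit: "Tumor assessments after PD per RECIST v1.1 or the initiation of new anti-cancer therapy (NACT) should not be used to derive the BOR".

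SAP 6.3 restates the data rule for the efficacy analyses. All scheduled and unscheduled scans "will be included in the efficacy analyses except for tumor assessments after the initiation of new anti-cancer therapy for the ORR and DoR endpoints", and the reader is referred to Section 4. Progression is not mentioned as a limit.

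For duration, SAP 4.2 says "DoR will be calculated for subjects who are responders, i.e., those who achieve a confirmed CR or PR". The formula is the earlier of the PD and death dates, minus the date of first PR or CR, plus 1. Responders without progression or death "will be censored at the date of the last tumor assessment". No rule for new anti-cancer therapy (NACT) appears there.

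Scans after progression are expected. Protocol 4.1.2 states "Treatment beyond progressive disease (PD) will be allowed as per iRECIST guidelines". In Protocol 7.1 the reason for stopping treatment is PD, qualified as "confirmed PD for subjects who continued treatment beyond PD, see Section 4.1.2". Protocol 8.1 has scans every 9 weeks "thereafter regardless of treatment delays until the EOT visit".

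**The concern.** Two adjacent paragraphs give different cut-offs for quantities that should agree. A programmer who follows them exactly will keep scans after progression for ORR and discard them for BOR. The number of ORR responders then need not equal the CR and PR rows of the BOR table. The additional responders also qualify for DoR under SAP 4.2, although their PD date precedes their response date.

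The response count drives the Phase 2 decisions. Under SAP 2.3, at least 2 of 16 responses open Stage 2 and at least 6 of 31 make a cohort promising. Under SAP 7.2, the safety data review committee looks at the number of responders and their DoR at the end of Stage 1. One differently classified subject can change either result.

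A related gap concerns DoR itself. SAP 6.3 says that Section 4 describes a NACT exclusion for DoR, but the DoR text in SAP 4.2 contains none. SAP Table 2 lists DoR among the Phase 2 primary endpoints.

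**Working it through.** **Step 1: reproduce the design.** Inputs from SAP 2.3 (same in Protocol 9.4): n1 = 16, continue if at least 2 respond; 15 more subjects, promising if at least 6 of 31 respond; null 10%, alternative 25%; stated power 80% and type I error 0.1.

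P(promising | p) = Σ over x ≥ 2 of Bin(x; 16, p) × P(Bin(15, p) ≥ 6 − x).

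At p = 0.10:

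| Stage 1 responses x | P(x of 16) | P(at least 6 − x of 15) | Product |
|---|---|---|---|
| 2 | 0.2745 | 0.0556 | 0.0153 |
| 3 | 0.1423 | 0.1841 | 0.0262 |
| 4 | 0.0514 | 0.4510 | 0.0232 |
| 5 | 0.0137 | 0.7941 | 0.0109 |
| 6 or more | 0.0033 | 1 | 0.0033 |

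The sum is 0.0788 (from unrounded terms), inside the stated 0.1. At p = 0.25 the same formula gives 0.805. The design is as described, and a search confirms that it is the minimax design.

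**Step 2: apply the ORR, BOR and DoR rules to two subjects.** Scans are on the planned 9-week schedule, in days after first dose, with no new therapy.

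| Sequence | ORR as written | BOR as written | DoR = PD date − response date + 1 |
|---|---|---|---|
| PD 63, PR 126, confirmed 189 | responder | PD | 63 − 126 + 1 = −62 days |
| SD 63, PD 126, PR 189, confirmed 252 | responder | SD | 126 − 189 + 1 = −62 days |

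With the first two scheduled scans as close together as the ±1-week windows permit (PD on day 71, PR on day 120), DoR is 71 − 120 + 1 = −48 days. In general, a response dated after PD cannot give a DoR above 0.

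**Step 3: effect on the decision rules.** The documents give no rate of confirmed response after progression, so the increments below are assumptions. They also assume that the 10% null refers to responses before progression.

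| Post-PD responses added to 10% (points) | P(promising) | P(stop at Stage 1) |
|---|---|---|
| 0 | 7.9% | 51.5% |
| +0.5 | 9.5% | 48.8% |
| +1 | 11.2% | 46.1% |
| +2 | 15.2% | 41.2% |
| +3 | 19.8% | 36.5% |
| +5 | 30.3% | 28.4% |

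P(stop at Stage 1) = P(Bin(16, p) ≤ 1). Solving P(promising) = 0.10 gives p = 0.1066, an increment of about 0.66 points. The gap between 7.9% and 10% absorbs anything smaller.

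**Step 4: look for a PD cut-off elsewhere.** The opening of SAP 4 applies RECIST v1.1 to ORR and BOR alike, without a cut-off. SAP 6.8.2 assigns responses after unconfirmed progression to the exploratory iRECIST response rate. Both suggest that the RECIST ORR was meant to stop at PD, but neither says so.

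**The case against.** The strongest reply is that the documents already tie ORR to BOR. SAP 4.1 speaks of each subject's overall response. Protocol 8.1 requires confirmation in order to assign a BOR of CR or PR. SAP 6.3.1 tabulates BOR under the ORR heading, and SAP 8 declares no change from the protocol. SAP 6.3 can be read as a summary that defers to Section 4. A negative duration would also be noticed at once.

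This is good evidence of intent, and the gap is most likely an omitted phrase. It does not settle the derivation. BOR is introduced in addition to ORR and does not define it. BOR is also specified under RECIST v1.1, yet the SAP still wrote out a PD cut-off for it. None of the other places cited adds one to ORR. Noticing an impossible duration would reveal the conflict without saying which responder count is right.

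A second reply is that the size rests on assumed rates and that the route is narrow: the Protocol 4.1.2 conditions must be met, treatment ends at confirmed PD, and the response itself needs confirmation at least 4 weeks later. That stands. The larger increments in the table are illustrations only, and nothing in the documents supports them.

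On DoR and new therapy, SAP 6.3 does remove scans taken after NACT, so the last assessment in SAP 4.2 becomes in effect the last one before NACT. That narrows the gap. The rule to which SAP 6.3 points is still missing, and a death after NACT has no stated handling for DoR.

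**Conclusion.** The concern holds: the ORR rule is wrong as written. Following SAP 4.1 and 6.3 exactly can produce an ORR responder whose BOR is PD or SD and whose DoR is negative, −62 days on the planned scan schedule. That result rests only on the SAP's own definitions and on the permission to treat and scan past progression.

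The effect on error rates is conditional. With a 10% pre-PD rate, the stated 10% type I error is exceeded only if post-PD confirmed responses add more than about 0.66 points. If they are rarer, it still holds. Even so, a single such subject can change a cohort's result at 1/16 or 5/31. The design and sample size are sound and unaffected. This should be corrected before database lock.

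**What to change.** 1. **SAP 4.1:** define ORR as the proportion of subjects whose BOR is confirmed CR or PR, using only scans up to the first RECIST v1.1 PD or the start of NACT, whichever is earlier.
2. **SAP 6.3:** use the same cut-off in the exception for ORR and DoR.
3. **SAP 4.2:** compute DoR only for these responders, with the event being PD or death after response onset. Add the NACT rule that SAP 6.3 refers to, including how death after NACT is handled. Censoring at the last tumor assessment before NACT, as in the primary column of Table 3 for PFS, would be consistent.
4. **SAP 2.3 and 7.2:** state that this RECIST count is the one used for the Stage 1 and Stage 2 decisions.
5. **SAP 6.8.2:** report responses after progression only under the iRECIST endpoints.

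The cost is a few sentences before database lock, with no new data. ORR may come out slightly lower than under the present text. With the cut-offs aligned, ORR and BOR agree, no negative DoR can arise from a response after PD, and the design keeps its exact type I error of 0.0788 and power of 0.805.
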